4.6.2. Assignment of trial subjects to treatment groups

642 Patients will be randomized by combinations of cardiovascular SOFA score level (0-2 or 3-4)
643 and presence or absence of oliguria. A stratified randomization procedure ⁴⁵ will be used to
644 generate the treatment assignment in order to achieve the best balance of combinations of
645 treatment, cardiovascular SOFA score level (0-2 or 3-4) and presence or absence of oliguria.

646 Stratification on the basis of SOFA Cardiovascular Organ Failure Score is necessary for the
647 following reason. A score of 3-4 identifies the subgroup of patients with profound
648 hemodynamic instability, manifested by hypotension requiring vasopressor support ⁴⁶.
649 Hypotension has been identified as an independent poor prognostic indicator in studies of
650 AKI; the cardiovascular organ failure being the only organ failure independently associated
651 with mortality by the SOFA score in patients with AKI ⁴⁷.

652 Patients will enter the treatment protocol immediately after randomization. The Executive
653 Committee will monitor and review the randomization process during the entire enrollment
654 phase of the study.

655

4.6.3. Concomitant medication

656 Consensus on the management of many other aspects of critically ill patients (e.g., use of
657 pulmonary artery catheters, selection of pressors) does not exist. The management of these
658 aspects of care (e.g., hemodynamic monitoring, selection of vasopressor agents) has not
659 been specified. In addition, these aspects of care will be monitored during the trial to assure
660 that significant differences are not present between groups. Similarly, we will monitor the use
661 of selected pharmacologic therapies, including medications that have been postulated to
662 have a salutary effect in acute kidney injury (e.g., fenoldopam and N-acetylcysteine), and
663 medications that are nephrotoxic and may prolong the duration of AKI (e.g., amphotericin,
664 aminoglycosides, cyclosporine, tacrolimus and radiocontrast agents).

665 Diuretic use will also be monitored. The impact on diuretic therapy on the outcome of
666 established AKI is minimal. While diuretic therapy may increase urine output in oliguric
667 patients, there is no evidence that these drugs alter dialysis requirements, renal recovery or
668 survival in AKI ⁵².

669

670 **4.7. Efficacy and safety variables**

671 **4.7.1. Measurement of efficacy and safety variables**

672 **4.7.1.1. Primary target variable**

673 The primary study endpoint is the overall survival in a 90-day follow-up period (90-day all
674 cause mortality).

675 **4.7.1.2. Secondary and other target variables**

676 • **Length of stay in intensive care unit and hospital**

677 Information on ICU and hospital stays will be documented. From admission to hospital
678 respective ICU until follow-up (by phone) at day 90, the location of the patient within the
679 hospital will be documented in the CRF. The following will be recorded for each patient

- 680 - Date and time of admission to hospital respective ICU
- 681 - Date and time of discharge from ICU including details of where patient is moving to
682 (e.g. general ward, high dependency unit, etc.)
- 683 - Dates, times and primary reason for all admissions to other wards in the hospital and
684 dates and times of discharges from other wards in the hospital
- 685 - Dates times and primary reason of all readmissions to ICU and dates and times of
686 discharges from ICU
- 687 - Date and time of discharge from hospital
- 688 - Dates, times and primary reason of all readmissions to hospital and dates and times
689 of discharges from hospital

690 • **Duration of renal replacement therapy [d]**

691 The duration of renal support will be defined as the number of days from the initiation of
692 renal replacement therapy to final dialysis treatment. Duration of renal support will be
693 censored if the patient is still dialysis dependent at the time of death. Duration of renal
694 support will be evaluated on the basis of both the mean number of days of renal support
695 and Kaplan-Meier survival, censored for patient death. The optimal outcome in acute
696 renal failure is the ability of the patient to return to his or her prior living situation not
697 requiring renal replacement therapy on an ongoing basis

698

699

700

701

702 • **Renal replacement therapy data**

703 The following data will be collected

704 - CVVHDF

- 705 ○ Hemodiafilter
- 706 ○ Blood flow
- 707 ○ Dialysate flow
- 708 ○ Replacement fluid rate
- 709 ○ Ultrafiltration rate
- 710 ○ Hours of therapy
- 711 ○ 24-h effluent volume

712 - Complications of therapy

- 713 ○ First use reaction
- 714 ○ Hypotension requiring discontinuation of treatment
- 715 ○ Air embolism
- 716 ○ Bleeding
- 717 ○ New onset of serious arrhythmia during treatment
- 718 ○ Iatrogenic fluid and/or electrolyte disturbance
- 719 ○ Seizures
- 720 ○ Catheter insertion complication

721 - Indications for termination of renal support

722 • **Recovery of renal function by day 28 and 60**

723 Recovery of renal function will be defined as lack of need for continuing dialysis support,
724 and will be classified as complete recovery, partial recovery or no recovery.

- 725 - Complete recovery of renal function will be defined as a serum creatinine that is
726 no more than 0.5 mg/dL greater than baseline.
- 727 - Partial recovery will be defined as a serum creatinine > 0.5 mg/dL greater than
728 baseline but not dialysis-dependent.
- 729 - Patients who remained dialysis dependent at study completion or at time of death
730 will be categorized as having no recovery of renal function.

731 Multiple studies have demonstrated that the majority of patients who recover renal
732 function following ARF do so within the first 4 weeks⁴⁰⁻⁴², justifying the use of the 28-day
733 and 60-day time points.

734

735

736 • **SOFA Organ Failure Scores at day 1-14, 21 and 28**

737 Non-renal organ system failures will be assessed on the basis of SOFA Organ Failure
738 Scores at days 1-14, day 21 and day 28 following randomization. Organ failure will be
739 defined as an individual SOFA organ failure score ≥ 2 . Parameters to be monitored will
740 include the maximum number of non-renal organ failures, the rates of individual non-renal
741 organ-system failures, the time course of non-renal organ failures, and the overall non-
742 renal SOFA score.

743 • **28-day, 60-day and 1-year mortality**

744 • **Cost analysis of renal replacement therapy**

745 *4.7.1.3. Safety analysis*

746 • **Incidence of adverse events and serious adverse events (including deaths)**

747 All adverse events (AEs) encountered during the clinical study will be reported in detail in
748 the source documents. Complications due to RRT will be documented in the eCRF, from
749 the randomization, throughout the clinical conduct and up to the follow-up visit on day 28.

750 *4.7.1.4. Add-on study*

751 To evaluate new biomarkers of acute kidney injury, investigate mediators modulating
752 mediators (pro- and anti-inflammatory mediators) and leukocyte function, an add-on study
753 will be performed. Blood and urine samples from recruited patients will be collected and
754 analysed.

755 *4.7.1.5. Description of visits*

756 • **Screening, Baseline**

- 757 - Demographic characteristics (date of birth, height, weight, sex)
- 758 - Inclusion and exclusion criteria
- 759 - Result of randomization
- 760 - Admission diagnosis, source of admission
- 761 - Cause of AKI
- 762 - APACHE II
- 763 - SIRS Score
- 764 - Hemodynamics (MAP, HR, CVP)
- 765 - SOFA-Score
- 766 - KDIGO-criteria
- 767 - Fluid balance
- 768 - Plasma NGAL

-
- 769 - Safety laboratory test
 - 770 - Blood and urine sampling for add-on study
 - 771 - Concomitant medication
 - 772 • **Daily visit day 1 until day 14, day 21**
 - 773 - Hemodynamics (MAP, HR, CVP)
 - 774 - SOFA-Score
 - 775 - KDIGO-criteria
 - 776 - Renal replacement therapy data
 - 777 - Fluid balance
 - 778 - Safety laboratory test
 - 779 - Blood sampling for add-on study (12 hours after randomization, 1,3 and 9 days
 - 780 after randomization
 - 781 - Complications
 - 782 - Mortality
 - 783 - Length of Stay
 - 784 - Concomitant medication
 - 785 • **Day 28**
 - 786 - Hemodynamics (MAP, HR, CVP)
 - 787 - SOFA-Score
 - 788 - KDIGO-criteria
 - 789 - Renal Replacement Therapy Data
 - 790 - Fluid balance
 - 791 - Safety laboratory test
 - 792 - Complications of RRT
 - 793 - Length of stay (ICU, Hospital)
 - 794 - Mortality
 - 795 - Duration of ventilator support
 - 796 - Number of days of RRT/RRT dependence
 - 797 - Serious adverse events
 - 798 • **Day 60**
 - 799 - Mortality
 - 800 - Length of stay (ICU, Hospital)
 - 801 - Economic and utility data of renal replacement therapy
 - 802 • **Day 90**
 - 803 - Mortality

-
- 804 - Length of stay (ICU, Hospital)
 - 805 - Duration of ventilator support
 - 806 - Number of days of RRT/RRT dependence
 - 807 - Serious adverse events
 - 808 - Economic and utility data of renal replacement therapy
 - 809 • **1 year follow-up**
 - 810 - Mortality
 - 811 - Length of stay (ICU, Hospital)
 - 812 - Duration of ventilator support
 - 813 - Number of days of RRT/RRT dependence
 - 814 - Economic and utility data of renal replacement therapy
 - 815
 - 816
 - 817

818 **Table 3: Investigations during the clinical trial**

Visit	S ¹	R ²	B ³	Days after Randomization				1 year Follow-up
				1-14, 21	28	60	90	
Inclusion and Exclusion criteria	X							
Randomization		X						
Demography			X					
Admission diagnosis, source of admission			X					
Cause of AKI			X					
APACHE II			X					
SIRS score			X					
Hemodynamics (MAP, HR, CVP)	X		X	X	X			
SOFA-Score	X		X	X	X			
KDIGO criteria	X		X	X	X			
Renal replacement therapy data Hemodiafilter, Blood flow, Dialysate flow, Replacement fluid rate, Ultrafiltration rate, Hours of therapy, 24-hour effluent volume Complications of therapy (first use reaction, hypotension requiring discontinuation or treatment, air embolism, bleeding, new onset of serious arrhythmia during treatment, iatrogenic fluid and/or electrolyte disturbance, seizures, catheter insertion complication Indications for termination of renal support				X	X			
Fluid balance / 24h urine volume	X		X	X	X			
Nutrition Management			X	X	X			
Concomitant Medication Pressors, fenoldopam, N-acetylcysteine, amphotericin, aminoglycosides, cyclosporine, tacrolimus, radiocontrast agents, diuretics			X	X	X			
Plasma-NGAL	X							
Safety laboratory test Complete blood count, potassium-, sodium-, calcium-plasma level, creatinine and BUN and eGFR, pH, bicarbonate, bilirubine	X		X	X	X			
Add-on study			X	X ⁴				
Mortality				X	X	X	X	X
Length of stay (ICU, Hospital)				X	X	X	X	X
Duration of ventilator support					X		X	X
Number of days of RRT/RRT dependence					X		X	X
Complications / number of non-renal organ failures					X		X	
Economic and Utility data						X	X	

¹ Screening

² Randomization

³ Baseline

⁴ randomization, 1, 3 and 7 days after randomization, 1 day after cessation of RRT

819 **4.8. Documentation**

820 All data relevant to the trial are documented soon after measurement by the investigator
821 responsible in the case report form supplied. Entering data may be delegated to members of
822 the trial team. The CRFs are signed by the investigator.

823 **4.8.1. Data management**

824 The IT infrastructure and data management staff will be supplied by the Department of
825 Anesthesiology, Intensive Care and Pain Medicine, University Hospital Münster. The trial
826 database will be developed and validated before data entry based on standard operating
827 procedures. The database is integrated into a general IT infrastructure and safety concept
828 with a firewall and backup system. The data are backed up daily. After completion and
829 cleaning of data, the database is locked and the data exported for statistical analysis.

830 Study staff enters the data into the trial database using doubled data documentation, and
831 the data entered is compared. Discrepancies and implausible values are clarified in writing
832 between the data manager and the investigator. These queries need to be answered without
833 unreasonable delay.

834 **4.8.2. Archiving**

835 All CRFs, informed consent forms and other important trial materials will be archived for at
836 least 10 years.

837 **5. Ethical and regulatory aspects**

838 **5.1. Independent ethics committee**

839 The clinical trial will not be started before approval of the competent ethics committee.

840 **5.2. Ethical basis for the clinical trial**

841 The present trial protocol and any amendments were and will be prepared in accordance
842 with the Declaration of Helsinki in the version of October 2008 (49th General Assembly of the
843 World Medical Association, Somerset West, Republic of South Africa).

844 All patients will receive standard intensive care therapy. As no pharmacological therapy for
845 AKI exists, the management of AKI remains primarily supportive, with renal replacement
846 therapy serving as a cornerstone of therapy in patients with severe kidney injury. None of the
847 patients in both groups ('early' and 'late' group) will be exposed to additional risks.
848 Participation in this study will be voluntary. Written informed consent will be obtained from
849 patients.

850 Data collection will be performed pseudonymously and the patient's name will not appear on
851 any case report form or in any other trial document submitted to the central data
852 management. All collected data will be kept confidential. Study protocol, patient information
853 and informed consent have been submitted to the ethics committees of the University of
854 Münster for appraisal. The principal investigator will inform the ethics committee about any
855 changes in the study protocol. The treating investigator will inform the patient about the
856 nature of the trial, its aims, expected advantages as well as possible risks. Each patient must
857 consent in writing to participate in the study. The patient must be given enough time and
858 opportunity to decide on participation and to clarify any questions before the beginning of
859 documentation of the study.

860 The informed consent will be signed by both patient and treating investigator. The original
861 document is kept by the investigator, whereas the patient receives a copy.

862 The legally authorized representative has to provide the written informed consent or in his
863 absence a declaration for inclusion in an emergency situation is to be signed by a consultant
864 physician who is not involved in the study and who is independent of the investigational team
865 (see 4.3).

866

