258 up following hospital discharge. It is felt, however, that based on the population being studied
259 and the ability to track patient survival using vital registry data, that loss to follow-up will not
260 impact significantly on the ability to track 90-day all cause mortality.

261

262 **2.3. Secondary and other objectives**

263 Secondary endpoints include:

- 264 • 28-day all cause mortality
- 265 • 60-day all cause mortality
- 266 • 1-year all cause mortality
- 267 • Recovery of renal function and requirement for hemodialysis after day 28 and day 60

268 Recovery of renal function will be defined as lack of need for continuing dialysis support, and
269 will be classified as complete recovery, partial recovery or no recovery. Complete recovery of
270 renal function will be defined as a serum creatinine that is no more than 0.5 mg/dL greater
271 than baseline. Partial recovery will be defined as a serum creatinine > 0.5 mg/dL greater than
272 baseline but not dialysis-dependent. Patients who remained dialysis dependent at study
273 completion or at time of death will be categorized as having no recovery of renal function.
274 Multiple studies have demonstrated that the majority of patients who recover renal function
275 following ARF do so within the first 4 weeks⁴⁰⁻⁴², justifying the use of the 28-day and 60-day
276 time points.

277 • Duration of renal support

278 The duration of renal support will be defined as the number of days from the initiation of renal
279 replacement therapy to final dialysis treatment. Duration of renal support will be censored if
280 the patient is still dialysis dependent at the time of death. Duration of renal support will be
281 evaluated on the basis of both the mean number of days of renal support and Kaplan-Meier
282 survival, censored for patient death. The optimal outcome in acute renal failure is the ability
283 of the patient to return to his or her prior living situation not requiring renal replacement
284 therapy on an ongoing basis.

285 • ICU length-of-stay

286 • Hospital length-of-stay

287 Both ICU and hospital length-of-stay will be defined based on the ICU and acute hospital
288 admissions during which the patient was randomized. Length-of-stay will be evaluated on the
289 basis of both the mean number of days of ICU/hospital stay following randomization and
290 Kaplan-Meier survival, censored for patient drop out or death. Hospital discharge will be

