 386 patients receiving care in the critical care units on a daily basis. After obtaining informed
 387 consent and check the randomization criteria, the patient will be registered and
 388 randomization will be carried out by the Institute of Biostatistics and Clinical Research
 389 Münster. Before initiating RRT, laboratory test will be performed and different variables will
 390 be documented including demographic data, APACHE II score, SOFA organ-system score,
 391 etc. In the 'early' group, RRT will be initiated immediately after randomization, whereas
 392 initiation of RRT in the 'late' group will be started after reaching stage 3 of the KDIGO
 393 classification and/or if absolute indications for RRT will be present. Laboratory tests will be
 394 analyzed and variables relevant for the assessment of illness severity will be recorded.

395 SOFA Organ Failure Score at different days, length of ICU stay, length of hospitalization, 28-
396 day all cause mortality, recovery of renal function and requirement for hemodialysis after day
397 28 and day 60, duration of renal replacement therapy, 60-day all cause mortality, 90-day all
398 cause mortality, cost analysis of renal replacement therapy, and 1 year mortality will be
399 documented at follow-up visits up to one year. * Absolute indications for the initiation of RRT
400 are 1) urea serum levels > 100mg/dl, 2) potassium serum levels > 6mmol/l and/or ECG
401 abnormalities, 3) magnesium serum levels > 4mmol/l and/or anuria/absence of deep tendon
402 reflexes, 4) blood pH < 7.15, 5) urine production < 200ml/12h or anuria, and 6) organ edema
403 in the presence of AKI resistant to diuretic treatment ⁴⁴.

404 **4.2. Discussion of trial design**

405 Renal replacement therapy is the main treatment option for AKI. To investigate the
406 appropriate time point of initiation of RRT, we will randomly assign patients to receive early
407 (KDIGO stage 2) or late (KDIGO stage 3 or if absolute indications for RRT are present)
408 initiation of RRT. A placebo group of patients with acute kidney injury withheld from RRT is
409 ethically not acceptable. The currently accepted, absolute indications for the initiation of RRT
410 are

- 411 1) urea serum levels > 100mg/dL,
- 412 2) potassium serum levels > 6mmol/L and/or ECG abnormalities,
- 413 3) magnesium serum levels > 4mmol/L and/or anuria/absence of deep tendon
414 reflexes,
- 415 4) blood pH < 7.15,
- 416 5) urine production < 200mL/12h or anuria, and

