6.1.2. Primary target variable

924 The effect of early initiation of RRT versus late initiation of RRT on overall survival in a 90-
925 day follow-up period will be assessed by comparing the randomized groups with a (two-
926 sided) Log-rank test.

927 The null hypothesis $H_0: S_0(t)=S_1(t)$ for all t is tested against the (two-sided) alternative H_1 :
928 $S_0(t')\neq S_1(t')$ for any t' , where $S_0(t)$ and $S_1(t)$ denote the overall survival function in the control
929 group and the experimental treatment group, respectively. If the difference in overall survival
930 is significant, the treatment effect will be estimated by means of the 90-day all cause
931 mortality rate in both treatment groups.

932 Further sensitivity analyses of the primary outcome are performed in order to address the
933 following issue. Study patients have a different baseline risk profile. This becomes apparent
934 especially in the control group with late initiation of RRT, where three risk groups may be
935 differentiated. There are “high risk” patients who die before the indication for RRT is reached
936 and “low risk” patients who survive the entire 90-day follow-up period and never show the
937 indication for RRT. The remaining “medium risk” patients (as expected about 80% of control
938 patients) show the indication for RRT at a certain time point in the 90-day follow-up period
939 and RRT is initiated. The efficacy of the experimental and the control treatment may differ
940 depending on the patients’ risk profile. Maybe “high risk” patients benefit from experimental
941 treatment with early initiation of RRT substantially compared to control treatment, whereas in
942 “low risk” patients both treatments are equally efficacious. Moreover it is of interest, if both
943 treatments differ in particular in the “medium risk” subgroup, i.e. in those control patients,
944 who actually received RRT, compared to the corresponding patients in the experimental
945 treatment group. In order to address these questions, multivariable statistical analyses are
946 performed using Cox regression. Overall survival is modelled as a function of baseline risk,
947 RRT treatment, and the interaction of baseline risk and RRT treatment. In three different
948 model approaches, RRT treatment is expressed in terms of (i) a time-dependent covariate
949 that impacts survival starting with the time of RRT initiation, (ii) the randomized treatment

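### The renal-recovery definition sorts deaths by dialysis status, so deaths before RRT, expected almost only in the late arm, count as recovery or drop out

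*Protocol*

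**What the plan says.** Section 4.7.1.2 sets the endpoint at days 28 and 60 (the Synopsis lists day 28 only) and states: "Recovery of renal function will be defined as lack of need for continuing dialysis support". It then forms three classes.

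- Complete recovery: creatinine no more than 0.5 mg/dL above baseline.
- Partial recovery: "Partial recovery will be defined as a serum creatinine > 0.5 mg/dL greater than" and then "baseline but not dialysis-dependent".
- No recovery: "Patients who remained dialysis dependent at study completion or at time of death".

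Section 2.3 gives the same definition, ending "completion or at time of death will be categorized as having no recovery of renal function". No class asks whether the patient is alive on day 28 or 60.

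Three other places bear on how this works by arm.

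- The text to Figure 1 (section 4.1.1) says "In the 'early' group, RRT will be initiated immediately after randomization, whereas" the late group waits for KDIGO stage 3 or an absolute indication.
- Section 6.1.2 divides the control arm into high-risk "patients who die before the indication for RRT is reached", low-risk patients who survive 90 days without reaching it, and a medium-risk remainder who reach it and start RRT. The size of the remainder is given in the words "patients (as expected about 80% of control".
- Section 6.1.3 rules out imputation of missing efficacy values.

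The Synopsis makes every analysis beyond the primary one exploratory.

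**The concern.** The definition does deal with death, but by dialysis status at the time. Two patients who die on the same day of the same illness are classed differently if one was on RRT and the other had not yet started. Whether a patient has started RRT is what the trial randomises, so the classification of deaths depends on the allocated arm. A comparison of recovery between arms could then show a difference where outcomes are the same, or hide a real one.

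The reference to study completion adds a second difficulty. Follow-up runs to one year, so a patient on dialysis at day 28 who stops later did not remain dependent at study completion, and it is unclear how that patient is classed at day 28.

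**Working it through.** **Step 1. Apply the classes to each kind of death.**

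| Death | Dialysis dependent at death? | Class as written | Arm |
|---|---|---|---|
| On RRT | yes | no recovery | both |
| After RRT was stopped | no | complete or partial, by creatinine | both |
| RRT never started | no | complete or partial, by creatinine; or missing if a day-28/60 value is required | almost only late |

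Most deaths in the last row would probably be graded partial. Section 4.3.1 admits patients with a 2 to 2.9-fold creatinine rise, and a doubling exceeds baseline by more than 0.5 mg/dL whenever baseline is above 0.5 mg/dL. A patient admitted on urine output alone could be graded complete.

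**Step 2. Inputs.** The protocol gives no figure for this endpoint. I use 250 recruited patients at 1:1 (sections 6.2 and 4.1), so 125 per arm, and about 80% of controls starting RRT (6.1.2), so about 20% never starting. Section 6.2 also mentions 260 recruits; that changes the counts slightly (0.20 × 130 = 26) but not the percentages.

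**Step 3. Size of the death-before-RRT route.** Never-starters: 0.20 × 125 = 25. Let s be the share of them who die; the protocol does not give it. Credited deaths = 25s, or 25s/125 = 20s percentage points.

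| s (assumed) | 0 | 0.25 | 0.50 | 0.75 | 1 |
|---|---|---|---|---|---|
| Patients | 0 | 6 | 12–13 | 19 | 25 |
| Points | 0 | 5 | 10 | 15 | 20 |

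The 20% refers to 90 days. Deaths before RRT by day 28 or 60 cannot exceed those by day 90, so 25 remains the upper bound.

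**Step 4. The other reading: these deaths are missing.** Assume 46% mortality in both arms, all other deaths on RRT and no survivor on dialysis. Early recovery is 54%. Dropping 5, 10 or 15% of the late arm gives 0.54/0.95 = 57%, 0.54/0.90 = 60% and 0.54/0.85 = 64%. The late arm still gains about 3, 6 or 10 points, because deaths on dialysis stay in as failures.

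**Step 5. What it could do to the comparison.** Assume the design mortality rates (37% early, 55% late, both at 90 days), no survivor on dialysis and every other death on RRT. Counting all deaths as not recovered gives 63% against 45%, or +18 points for early RRT. As written, the difference is 18 − 20s: +18, +13, +8, +3, −2 across the five values of s. If mortality were 46% in both arms, an artefact of 5, 10 or 20 points would reach two-sided p ≤ 0.05 with probability about 12%, 36% or 91% (two proportions, 125 per arm).

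**Step 6. The offsetting route.** Let b be the share of an arm that dies after stopping RRT. The net credit to the late arm is 20s + b(late) − b(early), in points. At s = 0.25 the sign reverses once b(early) exceeds b(late) by more than 5 points, about 6 of 125 patients. The protocol gives no value for b.

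**The case against.** The strongest reply is that no sentence assigns a class to a patient who dies without RRT. The wording speaks of continuing dialysis and of remaining dependent, which could be meant only for patients who had started. A patient dead before day 28 has no creatinine on that day, and section 6.1.3 forbids imputation, so such patients might be missing rather than recovered. This is a fair reading, and the grading as recovered is an inference from the classes. It does not remove the problem: step 4 shows that dropping them also favours the late arm. Nor is this simply detail left to an analysis plan, because the protocol already allocates deaths by dialysis status, in two places.

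A reader might infer that the bias always runs against early RRT. The documents do not support that. Deaths after RRT has stopped are credited in both arms, and could be more frequent in the early arm, where every patient is to start RRT.

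A reader might also take a particular size, such as 10 points, as expected. The roughly 20% is not split into deaths and survivors, and the late-arm triggers in section 4.6.1 are broad, so many dying patients may meet one first. Zero belongs in the range.

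Two further points stand. Counting death as not recovered makes the endpoint follow mortality closely: the 63% and 45% in step 5 are just one minus the mortality rates. That is why death should also be visible as its own category. And impact is limited, since mortality at 28 and 60 days is a separate endpoint.

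**Conclusion.** The point holds as a badly set definition of a secondary endpoint. Deaths on dialysis are failures; deaths off dialysis are graded as recovered or lost. Because deaths before RRT are expected almost only in the late arm, that route favours late RRT by 0 to 20 percentage points (0 to 25 of 125 patients). The range rests on 125 patients per arm and the protocol's expectation that about 80% of controls start RRT; the position within it cannot be determined from the document. The net direction, after deaths following the end of RRT are included, is not established. The reference to study completion does not fit a day-28 or day-60 endpoint. The analysis is exploratory, and the primary comparison of 90-day survival is not affected.

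**What to change.** In sections 2.3 and 4.7.1.2:

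- Define recovery at day 28 (and day 60) as alive and dialysis-free on that day, then grade it complete or partial by creatinine.
- Show death before the time point as its own category, and count it as not recovered in both arms whether or not RRT was ever started or had been stopped.
- Replace study completion with the named day.

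Cost: for day 28 this is a change of definition only, since Table 3 already schedules mortality, creatinine (in the safety laboratory test) and RRT dependence then. For day 60 it is not free: Table 3 and section 4.7.1.5 schedule mortality there, but neither creatinine nor RRT dependence. Either report only alive and dialysis-free at day 60, derived from RRT dates collected at day 90 (assuming the record holds the date of the last dialysis, which the definition of RRT duration requires), or add a day-60 creatinine.
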